## **Ethics and Registration**

GiC relies on the collection of sensitive health data, alongside academic achievement data from very young children in an early year setting. Undertaking the research requires a robust approach to research ethics. Given the level of risk involved, full reviews of the project ethics were sought from both health (NHS Bradford Teaching Hospitals Foundation Trust-IRAS 253681) and academic ethical review boards (University of Nottingham - CPMS 41579). The respective ethics review boards approved the study. Ethical approval was updated by both review boards in August 2020.

The trial will be independently and publicly registered by the University of Nottingham through the International Standard Randomised Controlled Trial Number organisation (ISRCTN) at www.controlled-trials.com.

Schools and parents will be provided with information sheets and privacy notices, which describe why and how the study will be conducted, detailed justification for the information collected and under what basis the data will be processed. Additional forms will be provided to the parents to allow them to withdraw their children from the study.

### **Data Protection**

The research will comply with the Data Protection Act (2018) and General Data Protection Regulations (2016). The project will work towards University of Nottingham and NHS Bradford Teaching Hospitals Foundation Trust ethical standards. We shall process data under the legal basis outlined in article 6(1)(e), "necessary for the performance of a task carried out in the public interest or in the exercise of official authority." For special category data our additional legal justification for processing, as required by article 9 of the GDPR, is article 9(2)(j), "processing is necessary for archiving purposes in the public interest, scientific or historical research purposes or statistical purposes in accordance with Article 89(1)."

The research team shall ensure that safeguards for managing personal data are in place. Specifically, we shall only process the minimum necessary data, utilise pseudonymisation techniques, ensure data is collected and stored in a secure manner as outlined by the University of Nottingham's *Handling Restricted Data Policy* and work to the University of Nottingham's research ethics standards. We shall also ensure that all research participants are provided with a privacy notice highlighting how we will use the data they provide.

In line with University of Nottingham standards, the university may store the data for up to 25 years after the project. Data will be stored securely in a password-protected SharePoint folder that is accessible to authorised persons only. Names of children and schools will not be released in associated research reports. The data will be shared with the Department for Education (DfE), the EEF, the EEF's

archive manager and in anonymised form with the Office for National Statistics and potentially other research teams, subject to the appropriate approvals. Data will be matched with the National Pupil database (NPD) for analysis during and after the trial. Further matching to the NPD and other administrative data may take place during subsequent research to better understand the impact of the project.

The trial parties have the following roles and responsibilities in the collection and management of data:

- The University of Nottingham will act as data controller throughout the evaluation period, up to and including successful submission of evaluation data to the archive (having passed internal FFT checks) and deletion of the data.
- Bradford Institute for Health Research and the University of Leeds will act as joint data controllers up to the point of data archiving and deletion. In the case of the achievement data, Bradford Institute for Health Research and the University of Leeds are data processors.
- Education Endowment Foundation will act as the data controller for the archive, which is managed on their behalf by FFT and held in the ONS Secure Research Service. The archive does not contain any information that can be used to directly identify an individual pupil. For example, the archive does not include names, addresses or dates of birth. The archive does contain the Pupil Matching Reference (PMR) which is an identifier used by the DfE to enable the linking of archive data to the NPD.

#### **Risks**

Business-as-usual schools will not be exposed to GiC intervention prior to study completion. Control schools will only receive business-as-usual services and supports. Threats to the delivery of the trial will be minimised via the following mechanisms:

- 1. Project delivery team will explain ramifications of participating in a randomised controlled trial to the school partners.
- 2. Schools will be required to sign an MOU indicating they are willing to participate in a randomised controlled trial and agree to the terms of contract agreement.

An online survey of control school will be used to monitor any potential treatment diffusion. However, it is not anticipated that the confounds outlined will take place in this study.

Other risks include loss of evaluation staff. However, the University of Nottingham has a large experienced staff team with ample expertise available as needed. Another risk includes failure to recruit an adequate number of schools. The timeline for recruitment is brief, given that schools will need to be in a position to have been randomised and the intervention promoted by mid-October in the 2019/20 academic year. To mitigate this risk, we suggest to over-recruit schools. Similarly, the work in September and October 2019 will be a short time scale to ensure that glasses can be ordered and delivered for the beginning of January 2020. Our process evaluation includes a robust fidelity of implementation protocol to minimize this risk. The risk analysis is presented below in **Error! Reference source not found.**6.

Table 6: Risk Analysis

Risk	Likelihood	Impact	Contingency plan
Inadequate schools recruited and reduced power	Moderate	Moderate	Compensation will be given to schools for completing pre and post-tests (£750 for controls and £250 for treatment groups). All schools are required to sign an MOU in spring 2021.
Different opinions on study design	Moderate	Moderate	UoN staff are experienced evaluators and work with intervention developers flexibly and expeditiously to ensure the study design is robust and meets standards for independence.
Data protection	Low	High	UoN have robust data protection and procedures in place
Attrition of schools and pupils	Low	Low	Appropriate compensation to schools. Allow ample time for testing and revisit schools if some pupils are absent on the data of testing. Ensure schools have a good understanding of the randomisation procedure, what the trial involves and ensure they will participate in the post-test evaluation activities even if they drop out from the intervention

Fidelity of implementation	Low	Low / Moderate	Development team monitor throughout process evaluation. Glasses will be ordered from November onwards and the provision of spare glasses to affected children will take place for the remainder of the school year via a daily check, likely linked to morning registration. Schools will implement a process for daily checking that children prescribed glasses wear them to accommodate their method of registration (such as by paper or via electronic means). They may also introduce various approaches to ensuring follow up appointments are met, including accompanying children to hospital or optometrist appointments as appropriate.
----------------------------	-----	----------------	----------------------------------------------------------------------------------------------------------------------------------------------------------------------------------------------------------------------------------------------------------------------------------------------------------------------------------------------------------------------------------------------------------------------------------------------------------------------------------------------------------------------------------------------------------------------------------------------------------------------------------------------------

**Evaluator (institution): University of Nottingham Principal investigator(s): [name]** 

## **Timeline**

Table 7: Key Dates and the Organisation Responsible for Study Activities

Dates	Activity	Staff responsible/ leading
November 2018-April 2019	Evaluation set-up completed, recruitment material finalised, ethics submitted	UoN/UoL/BIHR
April -June 2019	School recruitment, Expression of Interest and Memorandum of Understandings received	UoL/BIHR
July-August 2019	Trial protocol, agreement and trial registration completed	UoN
September 2019	Pupil withdrawal notifications received	UoL/BIHR
October 2019	Pupil data collected from settings and visual acuity and academic baseline testing completed	UoN/UoL/BIHR
October 2019  - November 2019	Randomisation completed	UoN
October 2019 - November 2019	Letters distributed to parents for eye appointments where appropriate, and glasses ordered	UoN/UoL/BIHR
December 2019-June 2021	Glasses delivered to schools, school monitoring of eye glass wear	UoL/BIHR
March-May 2021	IPE surveys distributed and case studies conducted	UoN
May-June 2021	Pupil visual acuity and academic post-testing completed	UoN
September 2021-June 2023	Optional: School monitoring of eye glass wear, glasses replaced as needed. School coordinators, teachers, parents instructed to notify the developer if glasses are lost or broken	UoL/BIHR
December 2021	Submission of draft report to the EEF	UoN
March-May 2022	Submission of final edited EEF report, submission of data to the EEF archive and updating of ISRCTN trial registry with results	UoN
September- December 2022	Optional longitudinal post-test: KS1 data collected from schools/Requested from NPD	UoN
May-June 2023	Optional longitudinal post-test: Pupil visual acuity post-testing completed, school monitoring of eye glass wear	UoL/BIHR
May-June 2024	Optional longitudinal post-test: Pupil visual acuity and academic post-testing completed, school monitoring of eye glass wear	UoL/BIHR/UoN

November 2022	Optional follow up: Analysis of Key Stage 1 data from NPD/ schools	UoN
February- March 2025	Submission of final addendum report	UoN

**Evaluator (institution): University of Nottingham Principal investigator(s): [name]** 

## Appendix I

Evaluator (institution): University of Nottingham Principal investigator(s): [name]

SAP last updated: January 2020

PROJECT TITLE	Glasses in classes: A cluster-randomised controlled to evaluate the effects of a school-based intervention improve academic achievement, visual acuity, and adherence to glasses wear in young children in a disadvantaged multi-ethnic community		
DEVELOPER (INSTITUTION)	NHS Bradford Teaching Hospitals Foundation Trust		
EVALUATOR (INSTITUTION)	University of Nottingham		
PRINCIPAL INVESTIGATOR(S)	[name]		
PROTOCOL AUTHOR(S)	[name], [name]		
TRIAL DESIGN	Two-arm cluster randomised controlled trial with random allocation at school level		
TRIAL TYPE	Efficacy		
PUPIL AGE RANGE AND KEY STAGE	Reception (4–5year olds), Early Years Foundation Stage		
NUMBER OF SCHOOLS	100		
NUMBER OF PUPILS	700		
PRIMARY OUTCOME MEASURE AND SOURCE	Reading achievement – Woodcock Johnson IV Letter- Word Identification Subscale		
SECONDARY OUTCOME MEASURE AND SOURCE	Reading achievement – Woodcock Johnson IV Word Attack; mathematics achievement – Woodcock Johnson IV Applied Problems; And visual acuity – logMAR		

SAP version history

VERSION	DATE	REASON FOR REVISION	
1.0 [original]	20/4/20	Published SAP version	

SAP last updated: January 2020

Contents

Introduction	3
Design overview	4
Sample size calculations overview	5
Analysis	6
Primary outcome analysis	6
Secondary outcome analysis	7
Subgroup analyses	7
Additional analyses	7
Longitudinal follow-up analyses	
Imbalance at baseline	8
Missing data	8
Compliance	8
Intra-cluster correlations (ICCs)	9
Effect size calculation	g

Evaluator (institution): University of Nottingham Principal investigator(s): [name]

SAP last updated: January 2020

Introduction

Eyesight development in children occurs within the first 7–8 years of life, with reduced VA in children indicating potential conditions including *refractive* error, amblyopia and/or strabismus (Bruce et al., 2018a; Daw, 1998; Dobson, 1993). There is growing consensus that vision problems may be a potentially treatable component of mathematics and reading difficulty (Collins et al., 2016; Granet, 2011; Kiely, Crewther, & Crewther, 2001; Levine, 1984; Lubkin, 1968; Solan et al., 2004). As part of the Child Health Promotion programme (Committee, 2009), the UK NSC recommends visual screening for children during their first year of school entry, with glasses wear being the principal treatment recommended for reduced vision. Children who fail to attend follow-up ophthalmic examinations and those who fail to adhere to glasses wear are unlikely to improve their level of VA, affecting their early reading and mathematics (Bruce et al., 2018a).

The purpose of this study is to examine the impact of a school-based intervention to improve glasses wear in children (which involves sharing vision screening results with school and provision of additional glasses to be kept in school) on their reading and mathematics achievement. The causal mechanisms of this effect such as attendance for eye appointments, adherence to glasses wear in young children following vision screening, and improvement in VA will also be examined. The effect of the intervention on academic achievement and VA in the child's first year (reception class) of school will be measured. This cluster randomised study will consist of two groups. The treatment group (50 schools), with approximately 350 pupils in need of glasses, will be randomised to receive the intervention over the academic year; the control group (50 schools) will receive business-as-usual care.

Ophthalmic treatment for the children participating in the trial will not change. However, the intervention schools will receive additional school-based support to promote glasses wear. This intervention has not been tested in the UK using a rigorous RCT approach although elements of the intervention have been studied previously within the Bradford setting (Bruce & Outwaite, 2013; Bruce et al., 2018a; Bruce, Sanders, & Sheldon, 2018b; Cassetti, Sanders, & Bruce 2019).

This statistical analysis plan outlines the analysis planned, discusses the study design and provides sample size calculations. It also addresses the primary and secondary outcome analyses, sub-group analysis, the additional mediation and longitudinal follow-up analyses, the handling of missing data and noncompliance issues, and finally effect size calculations.

Evaluator (institution): University of Nottingham Principal investigator(s): [name]

SAP last updated: January 2020

Design overview

Table 1: GiC Design Parameters

Trial design, including number of arms		Two-arm, cluster randomised		
Unit of randomisation		School		
Stratification variables (if applicable)		None		
Primary	variable	Reading achievement		
outcome	measure (instrument, scale, source)	Woodcock-Johnson IV Letter-Word Identification (Continuous)		
	variable(s)	Reading achievement, mathematics achievement and visual acuity		
Secondary outcome(s)	measure(s) (instrument, scale, source)	Woodcock-Johnson IV Word Attack (continuous) Woodcock-Johnson IV Applied Problems (continuous); logMAR (continuous)		
variable Baseline for		Reading achievement		
primary outcome	measure (instrument, scale, source)	Woodcock-Johnson IV Letter-Word Identification (Continuous)		
Baseline for	variable	Reading achievement, mathematics achievement and visual acuity		
secondary measure outcome (instrument, sc source)		Woodcock-Johnson IV Word Attack (continuous); Woodcock-Johnson IV Applied Problems (continuous); logMAR (continuous)		

Evaluator (institution): University of Nottingham Principal investigator(s): [name]

SAP last updated: January 2020

Sample size calculations overview

The trial has been designed to maximise the possibility of detecting an effect size of 0.2, within a very small geographical area of the Bradford Metropolitan area. The power analysis involved a number of sensitivity analyses conducted with a range of assumptions (varying ICCs, pre-post correlation, number of schools etc) and software – in particular MLPowSim (Browne, Golalizadeh Lahi, & Parker, 2009), PowerUpR (Bulus et al., 2018), and Optimal Design (Raudenbush, 2011). The analyses discussed below use PowerUpR which provides a more precise estimate than the more limited options available in Optimal Design. Power calculations are detailed in **Error! Reference source not found.** below.

Table 2: GiC Sample Size Estimates

		Protocol		Randomisation	
		OVERALL	FSM	OVERALL	FSM
Minimum Detectable Effect Size (MDES)		0.195	0.22	0.194	
Pre-test/ post-	level 1 (pupil)	0.88 ¹	0.88	0.88	0.88
test	level 2 (class)	-	-	-	-
correlations	level 3 (school)	0.62	0.62	0.62	0.62
Intracluster	level 2 (class)	-	-	-	-
correlations (ICCs)	level 3 (school)	0.15 ²	0.15	0.15	0.15
Alpha		0.05	0.05	0.05	0.05
Power		0.8	0.8	0.8	0.8
One-sided or two-sided?		Two-sided	Two-sided	Two-sided	Two-sided
Average cluster size		7	3	8	
	intervention	50	50	50	50
Number of schools	control	50	50	49	49
	total	100	100	99	99
	intervention	350	150	406	

¹ Villarreal (2015) undertook a test review of the WJIV standard battery of tests and found correlations in the range of .83-.95. In the Woodcock Johnson IV manual, test-retest correlations were between 0.83-0.95 for the age 7-11 group (p.94). However, these sort of test-re-test reliability analyses tend to be over very short periods (e.g. one day).

² We have selected an ICC of 0.15 as this represents a trade-off in that the schools are centred on a specific small geographical region, but on the other hand recognises that some EEF trials amongst Early Years have been higher at 0.17-0.19.

		Prot	Protocol		nisation
		OVERALL	FSM	OVERALL	FSM
Number of pupils	control	350	150	387	
	total	700	300	793	

With the above parameters, at the protocol stage, we estimated that it is possible to achieve an MDES of 0.195 for the main effect and 0.22 for FSM subgroup analysis. During recruitment we found that the number of children failing their initial vision screening was slightly higher than expected giving an average cluster size of 8 children in the study. Despite recruiting one school less than planned, the MDES remained effectively stationary at 0.194. The FSM estimate at randomisation will be updated once we receive the matched data from the DfE containing the FSM indicator.

Analysis

The analysis will examine the impact of the Glasses in Classes intervention in comparison to the business-as-usual control condition on the basis of intention to treat (ITT) using a two-level multilevel model using Maximum Likelihood estimation.

Error terms in linear regression are assumed to be independent. However, pupils are clustered within schools and are considered more similar than those pupils attending other schools, violating this key assumption. Multilevel modelling allows us to relax the independence assumption and represents a compromise approach between complete pooling approaches where all schools are treated the same within the model, and no pooling approaches where a separate model is fitted for each school. Multilevel modelling allows partial pooling where the effect of schools with little data are pooled towards the mean (Gelman & Hill, 2007, p252-259). Practically speaking multilevel models tend to provide the similar point estimates to complete pooling models, but have larger more appropriate standard errors and confidence intervals.

Primary outcome analysis

As discussed in table 1 above we will investigate the main outcome – the impact on reading achievement as measured by Woodcock Johnson IV Letter-Word Identification subscale. We will use the standardised score for both post and pre-test. As randomisation took place at the school-level, the post-test score will be modelled using a varying intercept model which is presented below follows:

$$\begin{aligned} \mathcal{Y}_{ij} &= \beta_{0j} + \beta_{1} Treatment_{ij} + \beta_{2} Pre - Test_{ij} + u_{0j} + \varepsilon_{ij} \\ & u_{0j} \sim N \; (0, \sigma_{school}^{2}) \\ & \varepsilon_{ij} \sim N \; (0, \sigma_{y}^{2}) \end{aligned}$$

This can be understood as follows. The post-test score for the i^{th} student in the j^{th} school is equal to the grand mean score (β_{0j}) , the impact of a binary indicator denoting treatment received (β_1) which is coded as 0 or 1, the impact of the mean-centred normally distributed pre-test (β_2) , the school-level error term (u_{0j}) , and finally the student-level error term (ε_{ij}) . The two error terms each receive their own probability distribution which are assumed to be normally distributed and centred on 0, with the two variance parameters estimated from the data $(\sigma^2_{school}$ and $\sigma^2_{v})$.

Secondary outcome analysis

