In sum, this CACE analysis will be used to assess the potential impact of random assignment and other covariates on compliance with the treatment. These estimates in turn will be used along with all covariates to predict the outcome of interest and therefore provide an unbiased estimate of the impact of compliance and non-compliance on the outcome. Hedge's g will be calculated to determine the effect size. Statistically insignificant and non-meaningful effects of the compliance variable will indicate that noncompliance in the study did not have an impact on the outcomes.

Intra-cluster correlations (ICCs)

Intra-cluster correlations (ICCs) will be calculated from a multilevel null model (i.e. one without the treatment or pre-test covariates, but including the school level) for the primary reading achievement outcome. The formula is presented below. As part of the appendices we will also provide ICC calculations for the secondary reading, mathematics and visual acuity outcomes.

$$ICC = \frac{\sigma_{school}^2}{(\sigma_{school}^2 + \sigma_y^2)}$$

Effect size calculation

EEF standard practice will be followed in reporting effect sizes (Hedges *g*). The formula is presented below:

$$ES = \frac{\overline{Y}^t - \overline{Y}^c}{\sqrt{(\sigma_{school}^2}^2 + \sigma_y^2)}$$

Effect size quantities will be computed from the Ime4 using the sim() function in the Applied Regression Modelling package (arm) in R to generate a posterior distribution from which 95% confidence intervals can be calculated.

References

- Bafumi, J. & Gelman, A. (2006) Fitting multilevel models when predictors and group effects correlate. 2006 Annual Meeting of the Midwest Political Science Association, Chicago, II.

 http://www.stat.columbia.edu/~gelman/research/unpublished/Bafumi_Gelman_Midwest06.pdf

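### The SAP fits its two-level models by maximum likelihood and names no small-sample reference, so inference on the school-level treatment effect is slightly too confident (minor)

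*SAP*

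**What the plan says.** The opening of the SAP's Analysis section sets the estimator for the intention-to-treat analysis: "using a two-level multilevel model using Maximum Likelihood estimation". It justifies multilevel modelling partly on the ground that such models "have larger more appropriate standard errors and confidence intervals".

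The secondary outcomes follow the primary model. The Subgroup analyses section specifies an FSM-by-treatment interaction model and also separate analyses of FSM and non-FSM pupils, whatever the interaction shows.

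Under Effect size calculation, the lme4 fit is passed to the sim() function of the arm package "to generate a posterior distribution from which 95% confidence intervals can be calculated".

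Neither document mentions REML, a t reference or a degrees-of-freedom method for the treatment effect. Neither states a normal reference. The protocol (Analysis plan, Main outcome) gives the same model without an estimator and leaves the detail to the SAP, so nothing overrides the choice of ML.

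**The concern.** Schools were randomised, so the treatment effect is judged mainly against variation between school means. ML estimates that variation as if the fixed effects were known. REML allows for having estimated them. With 99 schools the difference is small, but it always runs towards standard errors that are too small.

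The unstated reference distribution is a second gap. With about 97 degrees of freedom the two-sided 5% cut-off is 1.985, not 1.960. An analyst who reads the SAP literally could use either value.

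The primary outcome and all three secondary outcomes share this model. The separate FSM model may rest on fewer schools, so it is the most exposed. The SAP's stated reason for a multilevel model is an appropriate standard error, and the plan falls slightly short of that aim.

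**Working it through.** **Inputs (SAP, Table 2 and its notes).** Test level: "Alpha 0.05 0.05 0.05 0.05". Sidedness: "One-sided or two-sided? Two-sided Two-sided Two-sided Two-sided". Power: "Power 0.8 0.8 0.8 0.8". School ICC: "We have selected an ICC of 0.15 as this represents a trade-off". Pupil-level pre/post correlation: "level 1 (pupil) 0.88 ¹ 0.88 0.88 0.88". School-level correlation is 0.62. At randomisation there were 99 schools (50 v 49) with an average of 8 pupils. The FSM cluster size was planned as 3 and is blank at randomisation. The protocol's sample-size notes put FSM pupils at around a third.

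**Step 1: the plan's own figure.** With J schools, n pupils per school and proportion P treated,

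SE = sqrt{ [ICC(1 − r_school²) + (1 − ICC)(1 − r_pupil²)/n] / [P(1 − P)J] }

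- School part: 0.15 × (1 − 0.62²) = 0.0923.
- Pupil part: 0.85 × (1 − 0.88²)/8 = 0.0240.
- P(1 − P)J = (50 × 49)/99 = 24.75.
- SE = sqrt(0.1163/24.75) = 0.0686.
- MDES with t quantiles on 96 df: 0.1940. With normal quantiles: 0.1921. Stated: 0.194.

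The randomisation-stage MDES therefore reproduces with a t reference. The protocol-stage figures do not separate the two: 0.1959 (t) or 0.1939 (normal) against 0.195 overall, and 0.2237 or 0.2215 against 0.22 for FSM.

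The school part is 0.0923/0.1163 = 79% of the variance of the treatment estimate.

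**Step 2: approximation for the primary model.** With equal school sizes, the ML/REML ratio of standard errors is about sqrt((J − 2)/J) = sqrt(97/99) = 0.990.

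- ML with t: the effective cut-off is 1.985 × 0.990 = 1.965, so the actual level on 97 df is 5.2%.
- REML with normal: the cut-off is 1.960, so the level is 5.3%.
- ML with normal: the cut-off is 1.960 × 0.990 = 1.940, so the level is 5.5%. The width ratio to REML with t is 1.940/1.985 = 0.977, or 2.3% narrower.

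**Step 3: simulation with no true effect.** Each data set was fitted by ML and by REML, and each fit was referred to the normal and to t on (schools − 2) df. There were 15,000 data sets per row, except 20,000 in the second run of 3 FSM pupils per school. The Monte Carlo standard error is 0.16 to 0.19 points.

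| Model | Schools | SE ratio ML/REML | Width, ML-normal v REML-t | ML-normal | ML-t | REML-normal | REML-t |
|---|---|---|---|---|---|---|---|
| Primary, 8 per school | 99 | 0.9895 | 0.977 | 5.55% | 5.23% | 5.30% | 5.01% |
| Primary, unequal sizes | 99 | 0.9890 | 0.977 | 5.63% | 5.27% | 5.31% | 5.06% |
| FSM only, 3 per school | 99 | 0.9886 | 0.976 | 5.25% | 4.92% | 4.95% | 4.65% |
| FSM only, 3 per school, second run | 99 | 0.9886 | 0.976 | 5.34% | 5.07% | 5.10% | 4.84% |
| FSM only, each pupil FSM with chance 1/3 | 95 | 0.9874 | 0.975 | 5.97% | 5.69% | 5.71% | 5.41% |
| FSM only, uneven FSM shares | 75 | 0.9836 | 0.967 | 5.83% | 5.37% | 5.40% | 5.05% |
| FSM-by-treatment interaction | 99 | 0.9972 | n/a | 5.23% | 4.89% | 5.16% | 4.81% |

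In the first row the mean school variance is 0.0992 under ML and 0.1019 under REML, which is 0.0027/0.1019 = 2.6% lower. Only the ratio matters here.

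The FSM-only runs differ in their REML-t rate (4.65% to 5.41%), so part of the spread is Monte Carlo error. Within the same data, ML-normal exceeds REML-t by 0.50 to 0.78 points in those runs, against 0.54 and 0.57 in the two primary runs. The approximation in Step 2 gives 5.5% to 5.7% for 99 down to about 75 schools.

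**The case against.** The strongest counter-argument is that the effect of ML itself is trivial with 99 schools: 1% of the standard error and about 0.2 points of test level. No conclusion in the documents is shown to depend on it. That stands, and it is why this is minor.

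Four stronger readings are tempting, and the documents do not support them.

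- **A reader might infer that ML by itself gives the 2.3% and the 5.5%.** It does not. More than half of the shortfall comes from a normal cut-off. Changing to REML and nothing else leaves the level at about 5.3%.
- **A reader might infer that the SAP uses a normal reference, and so conflicts with its own MDES.** The SAP is silent on the reference. Its only stated interval method is simulation with sim(), and that procedure was not reproduced here. The 2.3% describes a 1.96-type interval and has not been shown for the sim() interval. The MDES is a planning figure, and the choice of t or normal moves it by only 0.002.
- **A reader might infer that all the subgroup models run at about 6%.** That is the top of the range, and it applies only to the separate FSM model. The interaction is largely a within-school contrast, and ML hardly touches it.
- **A reader might infer that the treatment standard error depends almost wholly on the school variance.** The share is 79% for the primary model. With about 2.67 FSM pupils per school the pupil part is 0.1918/2.67 = 0.0718, so the school share is 0.0923/(0.0923 + 0.0718) = 56%.

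It is also fair to say that a t-based interval would displace the planned sim() interval, so the amendment touches two places in the SAP. The case for acting survives. The error runs in one direction, it is shared by the primary and secondary outcomes, and an unstated reference leaves the analyst a choice worth about half a point of test level on identical data.

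**Conclusion.** The point holds as a minor one. ML is specified and no small-sample reference is planned. ML alone makes the primary standard error about 1% too small, with a test level of about 5.2%. ML with a normal reference makes primary intervals about 2.3% too narrow, with a level of about 5.5%. For the separate FSM-only model the same combination gives 5.3% to 6.0%, with intervals 2.4% to 3.3% too narrow. The interaction stays at about 5.2%.

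These sizes rest on the SAP's ICC and correlations and on normally distributed errors. They also rest on assumptions that the documents do not supply: a coefficient of variation of 0.6 for school size in the unequal-size runs, the spread of FSM pupils across schools, and the use of a 1.96-type cut-off. The FSM range reflects the uncertainty about FSM spread.

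**What to change.** 1. In the SAP's Analysis section, name restricted maximum likelihood in place of maximum likelihood for the primary, secondary, separate FSM and non-FSM, and ICC models.
2. State that the treatment p-value and 95% interval use a t reference with Satterthwaite or Kenward-Roger degrees of freedom. That is about 97 for the primary model and fewer where schools drop out of the FSM model.
3. Under Effect size calculation, base the interval on the REML fit and the same t reference instead of sim() draws alone, so that the p-value and interval agree.

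Both parts of the change are needed: REML with a normal cut-off leaves about 5.3%, while REML with t gives 5.0%. No new data are required. The cost is a short amendment in two sections of the SAP and intervals about 2% to 3% wider (for the primary model, 1/0.977 = 1.023).
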